### Informed Consent

Potential participant trainees will be informed of the training opportunity and the study. Heads of Department will be involved in the process. Trainee participants will be informed in detail about the nature of the education-intervention study; that the training offered offers no official qualification and will not be recorded in their annual review of clinical national training evaluation. All surgeons participating will be free to leave the study at any time. See Appendices 1 to 2 for detailed Information and Consent Forms.

### Withdrawal Criteria

Trainee participants are free to leave the study at any time. If this is the case for any participant, no effort will be made to recover any costs incurred. Data collected up to the point of withdrawal of consent will have been anonymized and securely stored and will still be held and included in data analysis.

### Baseline Data

#### Resident Trainees

- Age
- Sex
- Year of training
- Training Institution
- Number of MSICS surgeries performed as primary surgeon
- Number of MSICS surgeries assisted in or part performed
- Total number of other ophthalmic surgeries performed (disaggregated by type)

#### Attending Consultants (experts)

- Sex
- Training institution
- Number of MSICS surgeries performed as primary surgeon

### Randomisation

#### Sequence generation

The randomization sequences will be computer generated and administered centrally by a statistician based at the QUB who is independent of all other aspects of the trial. We will use block randomization (block size 2 or 4), with a separate sequence for each of the ten recruitment sites, to ensure balance. The statistician will generate the code / sequence (as a block of 2 or 4).

### Allocation Concealment

The statistician will not have access to information about subsequent allocation, and the individual potential participants. The PI, co-investigators, and participants will have no prior access to the random sequence.

### Randomization Implementation

Trainees within the same training institution, who have met the appropriate inclusion and exclusion (as detailed previously), will be eligible for randomization to the 'intervention' or 'control' arm. Each group of four trainee participants will be agreed by the Head of Training Program or Department.

For example (Blocks will be in groups of 4, 6 or 8 depending on the institution and the number of residents that meet the inclusion criteria):

A block of four potential participants is identified in Chittagong Eye Institute Training Center (CEITC), Bangladesh. Cards with the allocation or a block of four (two intervention and two control) were printed and placed in sealed opaque envelopes. Physically, in Bangladesh, a block of four identical envelopes (e.g. block number 11) will be selected. Participants will be invited by the Head of Department to pick one of the four envelopes. In this example, CEITC randomization block 11 allocation might be:

IRO1101	Intervention
IRO1102	Control
IRO1103	Control
IRO1104	Intervention

## Table 2: Orbis-FVR Training Program

Pre-Learning (one month in advance)

- Surgical video review

Pre-Course Assignment (one week in advance)

- Complete and record three full MSICS cases using the Philips Studio MSICS model eye and following the steps of the Sim-OSSCAR (Appendix 4).
- Upload the 3 recorded simulated surgical procedures to the Cybersight platform

The Orbis-FVR Virtual Reality MSICS simulator has 19 steps in total. Currently, 10 steps are animated and 9 are **interactive**, as follows:

1. *Patient Preparation – Animated Step*
2. *Conjunctival Peritomy – Animated Step*
3. *Paracentesis – Animated Step*
4. *Formation of the AC – Animated Step*
5. *Anterior Chamber Maintainer – Animated Step*
6. **Marking the Scleral Incision – Interactive Step**
7. **Scleral Incision – Interaction Step**
8. **Sclerocorneal tunnel – Interactive Step**
9. **Anterior Chamber (AC) Entry – Interactive Step**
10. **Continuous Curvilinear Capsulorrhexis (CCC) – Interactive Step**
11. *Hydrodissection – Animated Step*
12. **Mobilization of the nucleus – Interactive Step**
13. *Releasing the nucleus – Animated Step*
14. **Nucleus removal – Interactive Step**
15. *Cortex removal – Animated Step*
16. **IOL insertion – Interactive Step**
17. **IOL Dialing and Implantation – Interactive Step**
18. *Inspection of the wound – Animated Step*
19. *Closure of the wound – Animated Step*

### Course Overview

Participants must attend and successfully complete all sessions. All simulator tasks are to be completed in sequential order, in line with the course outline. A required minimum score of 85 points for each interactive step must be reached reliably three times in a row to advance to the next step in the course.

For each step within the simulation the following is recorded:

Step Time - The total time spent on a step including ALL attempts.

Pass / Fail - The interpreted pass or fail result of the last attempt of the step.

Step score - Each step is scored between 0 and 100 points, based on user performance in completing the surgical objective, taking into account any adverse events.

- Adverse events –For each step, if triggered, all of the adverse events are recorded.
- No. of attempts - The number of attempts (inc. resets) of the step.

### Course Content

- Each course will combine autonomous learning and live mentorship.
- Autonomous learning will consist of a series of 15-minute video presentations, which include:
  - Narrated demonstration video of specific VR step(s)
  - PowerPoint presentations

- Instrument use demonstrations
- Live mentorship will be delivered in two ways:
  - Local mentor who provides in-person mentorship
  - International mentor from technical advisory group provides live tele-mentorship

#### Content hosting

- All content will be hosted on the Orbis Cybersight Learning Management System platform (cybersight.org)
- Data will be randomized and anonymized by the Cybersight Program manager, who will not be involved in any other aspect of the research study.

#### Course delivery

##### Each day:

- Local mentor will facilitate introductions in each morning session. This will cover:
  - An overview of the day's training plan
  - Outlining the learning objectives for the day's training plan
  - Introduction of the content covered in the day's training plan
- Local mentor will also facilitate discussion and answer questions on autonomous content viewed in the morning and midday sessions
- Local mentor will provide periodic check ins throughout the day's session
- International mentor will provide tele-mentorship for the first hour of the 2-5pm session
- Trainees will do self-practice for the remainder of the afternoon session
- Each trainee will complete each interactive step on the VR simulator a minimum of 5 times with a reliability gate (3) and minimum score of 85
- Each trainee will complete at least 5 full cases on the VR simulator with a reliability gate (3) and minimum score of 85

## Course outline

Day	Morning 8:00 – 10:30	Midday 11:00 – 1:00	Afternoon 2:00 – 5:00
Monday	Introduction Orientation to simulator. Review of animated steps 1-5	Marking the scleral Incision Scleral Incision Sclerocorneal tunnel	Mentored practice Self-Practice
Tuesday	Introduction Review CCC	AC entry Hydrodissection Releasing the Nucleus Nucleus Removal Cortex Removal	Mentored practice Self-Practice
Wednesday	Introduction Review IOL Insertion IOL Dialling and implantation	Inspection of the wound Closure of the wound	Mentored practice Self-Practice
Thursday	Introduction Review of entire SICS procedure.	Putting it all together: Full Cases	Mentored practice Self-Practice
Friday	Introduction Assessment and Scoring	Final Review	

Attendance to be recorded as follows:

- Confirmation of three simulation video uploads pre-intervention
- Simulator use and assessment logs
- Attendance records taken per daily session
- Confirmation of three simulation video uploads post-intervention

## Outcomes

In the Fundamental Virtual Reality MSICS study, participants will be assessed on one occasion after recruitment (in addition to baseline), at one month: three simulation MSICS procedures recorded, anonymized and remotely assessed in a masked fashion (primary outcome). On the baseline and 1-month assessment, simulation MSICS procedures will be recorded (with masked assessment using the Sim-OSSCAR).

Primary Outcome – Orbis-FVR Study

**The primary outcome measure of the Orbis-FVR study will be the procedure specific repeated measures analysis of Sim-OSSCAR score performed three times at 1-month.** The analysis of the primary outcome measure will be based on the mean differences in the Sim-OSSCAR scores between the intervention and control groups. This score is derived from an assessment matrix or rubric of procedure specific and general microsurgical skill indices (see appendix 4). Each item in the matrix is graded on a modified Dreyfus score (novice, advanced beginner, and competent). The total possible score is 40 points.

Simulation assessment will be recorded using a standard microscope and recording device with all participants wearing similar latex-free surgical gloves. Recordings will be given an anonymous number to give no indication as to in which arm the surgeon is. Assessments of the surgical video will be conducted separately by two masked observers, watching the recorded surgery performed by the trainee at a separate time and place. Both observers are experienced eye surgeons and surgical trainers. Intra- and Inter-observer reliability studies will be conducted.

Secondary Outcomes / Qualitative Outcomes / Additional Exploratory Analysis:

1. Step-specific analysis: Secondary analysis of the primary outcome measure: mean differences in Sim-OSSCAR score for the seven interactive steps assessed (incision, tunnel, AC entry, CCC, mobilization, removal and IOL). Total possible score 14.
2. Assessment scores generated by Orbis-FundamentalVR MSICS simulator for two cohorts of surgeon: novice and expert (construct validity).
3. Self-reported confidence ratings (10-point Likert scale) in MSICS skills, and ophthalmic surgical skills.
4. Face validity assessment of Orbis-FVR simulator by international group of MSICS expert surgeons, performed through survey, using 5-point Likert scale.
5. Further qualitative study including acceptability assessment of Orbis-FVR simulator by international group of MSICS expert surgeons; and subjective improvement analysis and feedback by both experts and trainees.
6. Cost-effectiveness analysis of simulation-based training

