Outcome measures	
Assessments and follow-up time points are at baseline and 1 month.
 
Primary outcome measure: mean specific simulated surgical competency assessment score at one-month post-training intervention between groups (assessed using Sim-OSSCAR) (Appendix 4).
 
Secondary outcome measures:
 

• Assessment scores generated by Orbis-FVR Simulator pre- and post-intervention.

• Step-specific analysis: mean differences in Sim-OSSCAR score for the seven interactive steps assessed (incision, tunnel, AC entry, CCC, mobilization, removal and IOL). Total possible score 14.

• Self-reported confidence ratings (10-point Likert scale) in MSICS skills, and ophthalmic surgical skills

 
Further Exploratory Analysis:
 

• Construct validity study comparing scores generated by Orbis-FVR simulator between two cohorts of novice and expert MSICS surgeons.

• Face validity study subjectively assessing a group of expert MSICS surgeons' views of the Orbis-FVR simulator as representing MSICS

• Qualitative study of the acceptability and utility of the Orbis-FVR simulator as a training or assessment tool.

Population	The VR simulation surgical training, construct and face validity studies will be conducted in ophthalmology institutions in the Americas, Europe, Africa, and Asia. Participants will have follow-up assessments in their home training or work institutions in Bangladesh, China, Ethiopia, India, Mongolia, Togo, UK and USA.

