# Appendices

**Appendix 1 Participant Consent Form**

**Appendix 2 Participant Information Sheet**

**Appendix 3 Training Intervention**

**Appendix 4 MSICS Sim-OSSCAR**

**Appendix 5 Acceptability and Utility Survey**

**Appendix 6 Proposed Budget**

## Appendix 3. Training Intervention

Pre-Learning (one month in advance)

- Surgical video review

Pre-Course Assignment (one week in advance)

- Complete and record three full MSICS cases using the Philips MSICS model eye and following the steps of the OSSCAR (Appendix 4).
- Upload the 3 recorded simulated surgical procedures to the Cybersight platform

The Orbis-FVR Virtual Reality MSICS simulator has 19 steps in total. Currently, 10 steps are animated and 9 are interactive, as follows:

20. Patient Preparation – Animated Step
21. Conjunctival Peritomy – Animated Step
22. Paracentesis – Animated Step
23. Formation of the AC – Animated Step
24. Anterior Chamber Maintainer – Animated Step
25. Marking the Scleral Incision – Interactive Step
26. Scleral Incision – Interaction Step
27. Sclerocorneal tunnel – Interactive Step
28. AC Entry – Interactive Step
29. CCC – Interactive Step
30. Hydrodissection – Animated Step
31. Mobilization of the nucleus – Interactive Step
32. Releasing the nucleus – Animated Step
33. Nucleus removal – Interactive Step
34. Cortex removal – Animated Step
35. IOL insertion – Interactive Step
36. IOL Dialling and Implantation – Interactive Step
37. Inspection of the wound – Animated Step
38. Closure of the wound – Animated Step

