8	Capsulotomy / Capsulorrhexis start	Tentative; size and position are inadequate for nucleus density, incorrect capsulotomy position.	Mostly in control, slow initial start. Capsulotomy in correct position.	Correct and smooth start to capsulorrhexis. Delicate approach and confident control of cystotome.	
9	Capsulotomy / Capsulorrhexis completion	Tentative; size and position are inadequate for nucleus density, incorrect capsulotomy position. Radial tear	Mostly in control, few awkward or repositioning movements. Capsulotomy in correct position. Radial tear corrected.	Adequate size and position for nucleus density, no tears. AC depth throughout the capsulorrhexis.	
10	Hydro-dissection: Visible fluid wave and free prolapse of one pole of nucleus	Hydrodissection fluid not injected in quantity or place to achieve nucleus rotation or prolapse.	Fluid injected in appropriate location, able to prolapse one pole of nucleus but encounters more than minimal resistance.	Ideally see free fluid wave, adequate for free nuclear hydroprolapse or mechanical prolapse with minimal resistance.	
11	Injection of visco-elastic	Doesn't inject visco-elastic into eye	Injects insufficient visco-elastic. Injects only into PC or AC	Injects adequate visco-elastic into capsule bag behind nucleus, and AC	

12	Prolapse of nucleus partially into AC	Unable to dial nucleus into AC. Hooks anterior or posterior nuclear surface, nucleus rotates in the bag, iris and corneal touch.	Multiple attempts required to prolapse upper equator of nucleus into AC with more than minimal resistance. No corneal touch.	Prolapse of upper equator with minimal resistance. No damage to pupil and iris.	
13	Nucleus extraction	Damages endothelium, iris or capsule, unable to hold and extract nucleus, movements not coordinated. Pierces posterior capsule.	Removes nucleus after repeated attempts, more than one piece, might need wound extension prior to extraction.	Extracts nucleus with one or two attempts; proper wound size in relation to nuclear density.	
14	IOL insertion	Grips IOL incorrectly, inserts IOL incorrectly, multiple attempts.	Hesitant insertion of IOL, more than one attempt to insert	Inserts IOL into capsular bag efficiently, correctly, and in first attempt	

GLOBAL INDICES					

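### Is the stated maximum of 14 for the step-specific Sim-OSSCAR outcome wrong, given that the matching rubric rows can add to 16 or 18?

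*Combined protocol and SAP*

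**What the plan says.** In Outcomes, the secondary list opens with the "mean differences in Sim-OSSCAR score for the seven interactive steps assessed (incision, tunnel, AC entry, CCC, mobilization, removal and IOL). Total possible score 14". The Study Summary names the same seven steps and the same ceiling: "Total possible score 14".

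The primary outcome uses the whole rubric: "The total possible score is 40 points". Appendix 4 has 20 rows, each graded 0, 1 or 2.

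The simulator's own step list, in Table 2 and again in Appendix 3, is longer than seven: "Currently, 10 steps are animated and 9 are interactive, as follows". It includes "Mobilization of the nucleus – Interactive Step" and "Hydrodissection – Animated Step". The rubric has no row called mobilization; the nearest is item 12, "Prolapse of nucleus partially into AC". Capsulorrhexis is split into item 8, "Capsulotomy / Capsulorrhexis start", and item 9, its completion. The tunnel is split into item 5 (scleral) and item 6 (sclero-corneal).

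The statistical analysis section does not say which rows form each step score.

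**The concern.** The rubric is additive, so a subscore would normally be the sum of its rows. Nine rows match the seven step names, and nine rows at 2 points each make 18, not 14. The stated maximum therefore looks like a miscount, or like the trace of a selection rule that was never written down.

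If the rule is open, two analysts following the text could compute different outcomes. The weight of tunnel plus capsulorrhexis would differ between them, and so could the reported difference between arms. Masked grading protects the item scores but not a later choice of items, so in principle the score could be settled after results are known.

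**Working it through.** **Inputs.** Row scores (0 to 2) and row names come from Appendix 4. Step names come from Outcomes and the Study Summary. Simulator steps come from Table 2 and Appendix 3.

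**1. Reproduce the stated figures.**
- Full rubric: 20 rows x 2 = 40, as stated.
- Step-specific score: 7 steps x 2 = 14, as stated. This corresponds to one 0-2 score per named step.

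**2. Match rows to steps by name.**

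| Step | Rubric item(s) |
|---|---|
| Incision | 4 |
| Tunnel | 5, 6 |
| AC entry | 7 |
| CCC | 8, 9 |
| Mobilization | 12 (inferred) |
| Removal | 13 |
| IOL | 14 |

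Item 10 (hydrodissection) is left out because that simulator step is animated. Item 11 (viscoelastic) is left out because it is not a listed simulator step.

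**3. Enumerate the maxima.** Tunnel can be item 5, item 6 or both; CCC can be item 8, item 9 or both. That makes 3 x 3 = 9 row sets:
- one tunnel row and one CCC row: 7 x 2 = 14 (four sets);
- one pair kept whole: 8 x 2 = 16 (four sets);
- both pairs kept whole: 9 x 2 = 18 (one set).

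Averaging each pair also gives 14. So 14 fits the rubric, provided each step contributes a single 0-2 score.

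**4. Narrow the choice from the documents.** The simulator step is the sclerocorneal tunnel, which by name is item 6. Item 5 has no simulator step of its own. With tunnel set to item 6, only the CCC pair remains open: item 8 or item 9 (maximum 14), their average (14) or their sum (16).

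**5. Nine simulator steps against seven in the outcome.** The two interactive steps missing from the outcome's list are marking the incision and IOL dialing. Appendix 4 has no row named for either. The other seven appear in the outcome's list in the same order. The outcome concerns steps assessed on the rubric, so the two counts do not conflict.

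**6. Effect on the reported difference.**
- Weight of tunnel plus CCC: 4/14 = 29%, 6/16 = 38%, 8/18 = 44%.
- If arms differ by the same amount d on every item, the difference as a share of the maximum is 7d/14 = 8d/16 = 9d/18 = d/2, identical on all three scales.
- If arms differ by 1 point on items 5, 6, 8 and 9 and by nothing elsewhere, the difference is 2/14 = 14%, 3/16 = 19% or 4/18 = 22%. This is the extreme case.

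**7. Effect of choosing after the fact.** Simulated null trials used two-sample t-tests on normally distributed item means, 26 or 30 per arm, with the smallest p-value taken. The inter-item correlation was assumed to lie between 0.8 and 0.2, since the documents give none.

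| What is left open | False-positive rate, correlation 0.8 to 0.2 |
|---|---|
| Nothing (fixed score) | about 5% |
| Item 8 or item 9 only | about 5.4% to 6.5% |
| CCC as item 8, item 9, average or sum | about 5.5% to 6.9% |
| All four 14-point sets | 5.9% to 8.4% |
| Those four plus averaged, 16- and 18-point scores | 6.0% to 8.8% |

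The upper ends need a correlation of only 0.2, which is doubtful within a pair. The lowest-grade descriptions of items 8 and 9 are the same apart from the radial tear, and those of items 5 and 6 share the button-hole and premature-entry wording.

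**The case for a change.** The strongest case for acting is that this is a listed secondary outcome aimed at the very steps the simulator trains, that its definition is incomplete, and that listing item numbers would cost two wording edits. The arithmetic behind that case is right: adding all matching rows gives 18 or 16, and every row set that reaches 14 drops one row from each pair unless pairs are averaged. It is also true that masking does not govern the choice of items and that matching mobilization to item 12 is an inference.

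What stands is a gap in detail. What does not stand is that 14 is wrong, or that 18 is the natural default. A total of 18 would override a ceiling the plan gives twice and would count a tunnel row that the simulator step does not name. The larger false-positive figures require an analyst to try four to seven versions of the score and report the best one. Nothing in the plan suggests this, and it is not the consequence of an ordinary reading. Nor is summing, selecting or averaging shown to be the better method, so a change of scale would bring no demonstrable gain.

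**Conclusion.** The stated maximum is consistent with the rubric: seven steps at 2 points each, one score per step. The plan omits the row-level rule for the tunnel and capsulorrhexis pairs. Any sensible one-score-per-step choice gives a sound secondary result from item scores already graded under masking for the primary outcome.

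If tunnel is read as item 6, the remaining ambiguity is confined to capsulorrhexis. Even deliberate selection there would move a 5% error rate to no more than about 6.9%. The conclusion rests on matching rows to steps by name, on item 12 standing for mobilization, and on the assumed correlations.

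The outcome is a secondary analysis in a study that the Executive Summary calls a pilot. The 40-point primary score, its analysis and the sample size do not depend on it. This is a gap that analysts fill in the ordinary course of their work, and it does not call for a change to the plan.

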## Analysis

Statistical analysis

The primary outcome measure (mean Sim-OSSCAR score at 1 month) will be analyzed using a t-test. Performances will be compared between intervention and control groups: these are a continuous variable in each group. We will compare these mean Sim-OSSCAR^1 scores by t-tests (which is unadjusted) and linear regression (adjusting for training center as a fixed effect). An alpha level of  $p < 0.05$  will be considered statistically significant, and a kappa coefficient of  $\geq 0.75$  for inter-rater agreement is considered

excellent.

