## Sample size

Based on pilot and published data we anticipate the mean Sim-OSSCAR score to be 10/40 (standard deviation (SD) 6 points) at baseline. We anticipate an effect size of 2.5 SD in the mean Sim-OSSCAR between groups. We assume a correlation between these observations of 0.8. Variation between clusters (training institutions) will be accounted for with a co-efficient of variation of 0.5.

Therefore, a sample of 52 individuals in total (26 in each arm) would have 80% power and 95% confidence to detect a difference of 15 points (2.5SD). We will recruit 60 participants for the Orbis-FVR training study to provide 8 extra participants as we anticipate a moderate loss to follow-up.

We and our collaborators consider this sample size of 60 participants to be feasible within the available time and financial resources. It would take longer (an extra academic year) if we needed to recruit many more, and if the impact of COVID-19 on training continued throughout the recruitment year.

For the construct validity of the FVR assessment capacity, we will recruit a total of 5 experts and 5 novices from participating centers. Sample sizes of content, face and construct validity study are based on data from recent validation studies of ophthalmic simulation surgical competency assessment rubrics. Additionally, as we predict a large differences between the two participating groups, small cohort numbers suffice. For face validity, we will recruit ten experts from multiple centers, likewise, this was determined based on data from similar face validation studies.

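### Randomisation is stratified by site, but the plan names an unadjusted t-test for the primary outcome and does not rank it against its own site-adjusted regression

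*Combined protocol and SAP*

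**What the plan says.** Under Randomisation, Sequence generation, allocation is in blocks, "with a separate sequence for each of the ten recruitment sites, to ensure balance". The example under Randomization Implementation puts two intervention and two control places in a block of four, so arms are balanced 1:1 within site.

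The primary outcome is described in three places:

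- **Statistical analysis:** "The primary outcome measure (mean Sim-OSSCAR score at 1 month) will be analyzed using a t-test". Two sentences later the plan says it will compare the mean "scores by t-tests (which is unadjusted) and linear regression (adjusting for training center as a fixed effect"). It sets one significance level and gives no ranking of the two methods.
- **Outcomes, Primary Outcome:** the measure is "the procedure specific repeated measures analysis of Sim-OSSCAR score performed three times at 1-month", but the next sentence says the analysis "will be based on the mean differences in the Sim-OSSCAR scores between the intervention and control groups".
- **Study Summary, Outcome measures:** "mean specific simulated surgical competency assessment score at one-month post-training intervention between groups".

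The Sample size section expects institutions to differ: "Variation between clusters (training institutions) will be accounted for with a co-efficient of variation of 0.5".

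**The concern.** The site-adjusted analysis is already planned. What is missing is the hierarchy. On one reading the t-test decides, and the deciding analysis ignores the randomisation strata. On the other reading the two methods are equal, and one primary outcome has two p-values with no rule for when they disagree.

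Balancing arms within site removes site differences from the comparison. An unadjusted t-test still counts them as noise. The consequence is lost precision and power. It does not inflate false positives.

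Precision matters here for two reasons. The Executive Summary says the results will inform the design of a future multi-center trial. The Cost-effectiveness section divides cost by the difference in scores, so uncertainty in that difference carries into the cost-effectiveness ratio.

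**Working it through.** **Inputs from the plan.** Baseline mean 10 and SD 6, difference 15 points, 52 analysed (26 per arm) of 60 recruited, and a coefficient of variation of 0.5 between institutions (Sample size). Alpha is 0.05 (Statistical analysis), taken as two-sided because the plan does not say. There are ten sites (Sequence generation) or nine (Study Setting), so both were tried.

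**The plan's own figure.** The simple two-means formula gives 2 × (1.96 + 0.84)² × 6² / 15² = 2.5, so 3 per arm, not 26. With 26 per arm and SD 6, 80% power corresponds to 2.80 × 6 × √(2/26) = 4.7 points. This mismatch is a separate matter and does not affect the present point. It does show that differences of around 5 points are where 52 trainees would be tested.

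**Assumption on site variation.** The plan does not say which mean the coefficient of variation applies to. Applied to the baseline mean, the site SD is 0.5 × 10 = 5. If SD 6 is within-site, the site share of variance (ICC) is 25/(25 + 36) = 0.41. If SD 6 is the total, the within-site SD is √(36 − 25) = 3.32 and the ICC is 25/36 = 0.69.

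**Analytic check (within-site SD 6, site SD 5).** With balance within site, the true variance of the difference is 2 × 36/26. The t-test estimates roughly 2 × 61/26.

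- t-test half-width: 2.009 × √(61 × 2/26) = 4.35 points
- adjusted half-width: 2.02 × 6 × √(2/26) = 3.36 points

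**Simulation.** Sixty trainees were randomised 1:1 within ten sites of six, 52 were kept at random, and each setting had 3,000 to 6,000 runs. The 5-point difference is illustrative and is not in the plan. Ranges cover repeated runs.

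| Setting | 95% half-width, t-test v adjusted | Power at 5 points, t-test v adjusted |
|---|---|---|
| Within-site SD 6, site SD 5 | 4.25–4.28 v 3.38–3.40 | 65–68% v 81–84% |
| Total SD 6, site SD 5 | 3.21–3.22 v 1.87–1.88 | 93% v 99.9% |
| Within-site SD 6, site SD 2 | 3.50 v 3.40 | 81% v 82–83% |
| Within-site SD 6, no site variation | 3.33 v 3.39 | 84% v 82% |

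- **Type I error of the t-test:** about 2% in the first setting and 0.4% in the second. The adjusted test stays near 5%.
- **Disagreement at p<0.05, 5-point difference:** 16–17% of trials in the first setting, nearly always with only the adjusted test significant. It is about 5% at site SD 2 and 4% with no site variation.
- **At 15 points:** 100% power for both tests in every setting.
- **Bias:** below 0.06 points throughout.
- **Nine sites:** half-widths agree to within 0.1 point.

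**Check by ICC.** A second simulation held the total SD at 6, with 52 trainees in nine sites balanced within site. It does not depend on how the coefficient of variation is read.

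| ICC | Full 95% width, t-test v adjusted | Ratio | t-test type I error |
|---|---|---|---|
| 0 | 6.64 v 6.67 | 1.00 | 5.0% |
| 0.1 | 6.63 v 6.34 | 1.05 | 4.1% |
| 0.2 | 6.58 v 5.96 | 1.10 | 3.2% |
| 0.41 | 6.51 v 5.13 | 1.27 | 1.7% |
| 0.69 | 6.42 v 3.72 | 1.73 | 0.3% |

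Site SD 2 with within-site SD 6 is an ICC of 4/40 = 0.1, and the two tables agree there.

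**The case against.** The opening sentence of the Statistical analysis section attaches only the t-test to the primary outcome, so a natural reading is that the t-test is primary and the regression supportive. The regression will be run anyway, so its narrower interval will exist whatever it is called. At the planned 15-point difference the verdict cannot change. The larger figures rest on an assumed site SD, and an ICC of 0.69 looks high when eligibility restricts everyone to near-zero MSICS experience. The t-test errs on the cautious side. The repeated measures wording is largely resolved by the sentence after it.

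Most of this stands as a limit on size. The error is conservative, nothing is lost at 15 points, and the gain runs from slightly negative to material depending on site variation that the documents do not settle.

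It does not remove the point. If the t-test is primary, the headline analysis ignores the strata used to randomise. If it is not, the plan does not say what is. Producing both intervals does not settle which one supports the trial's conclusion.

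**Conclusion.** The concern holds. The plan stratifies by site, plans the analysis that matches, and does not make that analysis primary. When sites differ, the t-test interval is too wide: about 5% at an ICC of 0.1, 10% at 0.2 and 27% at 0.41. If the coefficient of variation of 0.5 applies to the baseline mean and SD 6 is within-site, the half-width is about 4.3 points instead of 3.4.

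The direction is certain whenever sites differ. The size depends on the assumed site SD. The estimate is unbiased and the false-positive rate is not inflated, so the trial's validity is not in question. What is affected is the precision of the headline result, power for differences well below 15 points, and the absence of a rule if the two tests disagree. The change should be made.

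**What to change.** In Statistical analysis, state that the primary analysis is a linear regression of each trainee's mean 1-month Sim-OSSCAR score on arm, with training center as a fixed effect, and that the unadjusted t-test is supportive.

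In Outcomes, replace the repeated measures description with one mean per trainee over the three procedures and two observers, in line with the Study Summary and Statistical analysis. Settle whether there are nine or ten sites, since this fixes the number of site terms.

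The cost is wording only, with no new data. Site terms use 8 to 9 degrees of freedom (residual 41 to 42 instead of 50, critical t 2.02 v 2.01). If sites do not differ at all, the half-width grows from 3.33 to 3.39 points, about 2%.

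A separate option, which does not follow from the stratification, is to add the baseline score already collected as a covariate. If its within-site correlation with the 1-month score is 0.8 (one possible reading of the correlation in Sample size), the half-width falls to about 3.4 × √(1 − 0.64) = 2.0 points (simulated, 2.1). At 0.5 it is 3.4 × √0.75 = 2.9, and at 0 there is no gain.
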